## **STATISTICAL ANALYSIS PLAN**

**TITLE: Evaluation of Vitamin D With And Without Hormonal Contraception on Sexual Function in Women With Polycystic Ovary Syndrome**

**INVESTIGATORS:** [name], MMM; [name]; [name], [name]; [name]

October 14, 2016

NCT02865187

Statistical analysis will consist of 1) comparison of baseline with 6 month scores on FSFI total and subscale scores, and comparison of baseline with 6 month Vitamin D levels. Paired t-test will be used to determine degree of change and statistical significance of change scores.

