INVESTIGATORS: [name], MMM; [name]; [name], [name]; [name]

BACKGROUND:

Polycystic ovary syndrome (PCOS) is the most common endocrine disorder among reproductive age women with a prevalence as high as 15% using Rotterdam diagnostic criteria.¹ PCOS is a heterogeneous clinical disorder characterized primarily by chronic anovulation and hyperandrogenism.² A number of other metabolic and health complications are associated with PCOS including obesity, insulin resistance, dyslipidemia, type 2 diabetes, cardiovascular disease, and endometrial cancer.³

The clinical symptoms of PCOS including menstrual dysfunction, infertility, hirsutism, alopecia, acne, and the possible increased risk of diabetes and cardiovascular disease have been reported to be significant contributors to psychological morbidity and impact health-related quality of life (HRQoL)^{4,5} including depression and anxiety,^{6,7} suicide attempts,⁸ body dissatisfaction,⁹ eating disorders,¹⁰ lower overall health-related quality of life¹¹ and diminished sexual satisfaction.^{12,13}

For women with PCOS, the changes in physical appearance and the associated mood disorders appear to be deleterious for sexual function.⁶ Previous research in this area is scant, and what has been done reveals a large number of women with PCOS (60%) reporting sexual dysfunction and that the domains of desire and arousal are most commonly affected (in 98% - 99% of cases). Using the Changes in Sexual Functioning Questionnaire (CSFQ), others have reported that women with PCOS were similar to control women in the number of sexual thoughts and fantasies and in the frequency of sexual intercourse, but differed significantly with lower orgasm/completion scores than control women.¹³ The existing research is limited by the study populations used, which have consisted of infertile women with PCOS who have a high prevalence of sexual dysfunction that may be more related to infertility and not an underlying sexual dysfunction, and by the possible impact of depression and psychotropic medications on sexual dysfunction.

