The specific contribution of estrogens and progestogens in oral contraceptives is not fully understood, particularly the latter as it has variable potency and androgenicity. In general, the most commonly used progestins are the 19-testosterone derivatives. Newer oral contraceptives, such as drospirenone, norgestimate, and desogestrel, contain less androgenic progestins. Drospirenone is a 17-alpha spironolactone derivative progestin with antiandrogenic and antiminerlocorticoid activity. Studies have shown various benefits of combined hormonal contraceptives for PCOS patients who are not pursuing fertility, e.g., management of endocrine and metabolic profiles, androgen levels, and endometrial cancer.⁵

Vitamin D supplementation has also been reported to improve glucose metabolism and menstrual frequency in PCOS women¹⁷ and since Vitamin D deficiency is closely linked to PCOS and depression, its supplementation has been suggested to possibly play an important part in the treatment of PCOS and HRQoL and perhaps SDy.¹⁸

As such, the goal of this study is to evaluate the prevalence of sexual dysfunction and assess the impact of treatment using oral contraceptives with Vitamin D on SDy in absence of depression. We anticipate this may provide a new treatment strategy in SDy issues for women with PCOS.

OBJECTIVES:

1. To evaluate the prevalence of sexual dysfunction (SDy) in women with Polycystic Ovarian Syndrome (PCOS)
2. To determine the effects of Vitamin D therapy, with and without hormonal contraceptives, on SDy in women with PCOS in the absence of depression.

METHODS:

The study will enroll 60 women diagnosed with PCOS and reporting SDy at the Wright State Physicians (WSP) OB-GYN Practice and the WSP Family Medicine Practice.

All participants will take vitamin D 600IU/day (as recommended by the National Institutes of Health's Office of Dietary Supplements) and will choose between hormonal and non-hormonal contraceptive methods (target of 30 participants in each group). Participants will complete three study visits (Initial, Month 3, and Month 6). Vitamin D levels will be drawn at the beginning of the study and again at 3 and 6 months after initiation of vitamin D therapy. Each participant will be asked to complete the Female Sexual Function Index (FSFI) and the Beck Depression Inventory (BDI) prior to initiation of treatment and again at 6 months.

Inclusion / Exclusion Criteria:

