Women will be included in the study if they meet the following inclusion criteria and none of the exclusion criteria listed below:

Inclusion criteria:

- 1) Are reproductive age from 18-40 years old;
- 2) Have a diagnosis of PCOS using the revised 2003 Rotterdam European Society for Human Reproduction (ESHRE) criteria in which the following are present:
 - a) Oligomenorrhea (cycles lasting longer than 35 days) or amenorrhea (fewer than 3 cycles in the past 6 months);
 - b) Either clinical signs of hyperandrogenism (hirsutism with a Ferriman-Gallwey score of more than 7 or obvious acne or pronounced alopecia) or an elevated total testosterone (>2.0 nmol/L); **or**

- c) Poylecystic appearing ovaries.
- 3) Report SDy according to the FSFI; and
- 4) Have no evidence of severe depression as measured by the BDI >30.

Exclusion criteria:

- 1) Patients with chronic medical illness, such as, diabetes mellitus, hypertension and previous venous embolism
- 2) Are taking any prescription medications for at least 3 months prior to entering the study, with the exception of allergy and occasional pain medications
- 3) Have other etiologies of anovulation and hyperandrogenism (e.g., Cushing's, thyroid dysfunction, elevated prolactin levels, signs of congenital adrenal hyperplasia)
- 4) Have any contraindications to hormonal contraception

Recruitment:

Participants will be recruited from the Wright State Physicians Obstetrics and Gynecology and Family Medicine practice offices. The opportunity to be involved in this research project will be approached at their clinic visit with the physician if the patient meets selection criteria. A consent form will be given and the study will be discussed.

In addition, print advertisements will be placed in the local Reach magazine to recruit patients in the Dayton area.

Stipends:

Participants will receive a stipend in the form of a MasterCard gift card for their time and travel. After each completed study visit the participant will be provided with a gift card -in the amounts as follows: \$50 at Visit 1 and Visit 3, and \$35 at Visit 2 for a maximum per patient compensation of \$135.

HUMAN SUBJECTS PROTECTION:

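### The SAP tests the FSFI total and subscales for significance with no primary FSFI outcome, alpha or multiplicity rule: about 8–28% risk of a false FSFI finding (assuming two-sided 0.05, 3–6 subscales, correlation 0–0.9)

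*SAP*

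**What the plan says.** The analysis text of the SAP is two sentences. The first lists a "comparison of baseline with 6 month scores on FSFI total and subscale scores" and a "comparison of baseline with 6 month Vitamin D levels". The second says: "Paired t-test will be used to determine degree of change and statistical significance of change scores". The total, the subscales and vitamin D level stand on an equal footing.

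The protocol has no statistics section. Its second objective is "To determine the effects of Vitamin D therapy, with and without hormonal contraceptives, on SDy in women with PCOS", restricted to women without depression; it names no FSFI score. The third inclusion criterion is "Report SDy according to the FSFI", again with no domain singled out. The two objectives are not ranked. Neither document gives a primary outcome, a significance level, sidedness, a testing order, a multiplicity adjustment or the number of FSFI subscales.

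**The concern.** Several significance tests address one objective and nothing ranks them. Any of them could be put forward as the test of objective 2, including a subscale that is significant when the total is not. The chance that at least one FSFI score appears to change when none has is then higher than the level used for each test. A reader holding the SAP can see that several tests were planned, but not which one was meant to decide the question. What is at stake is whether a claim that sexual function changed on vitamin D rests on one test chosen in advance or on the most favourable of several.

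**Working it through.** The documents state no alpha, power or error rate, and the sample of 60 has no derivation, so there is no plan figure to reproduce.

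**Inputs from the documents.** One change score per FSFI scale (baseline and 6 months); paired t-tests; 60 women planned, with a target of 30 in each self-chosen contraceptive group.

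**Assumptions, none given in the documents.** Two-sided 0.05 per test; k = 3 to 6 subscales; total equal to the unweighted sum of the subscales; common correlation ρ between subscale changes from 0 to 0.9; all 60 women analysed together without dropout; zero true mean change.

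**Step 1, rough ceiling.** If all k + 1 FSFI tests were independent, the chance of at least one false result would be 1 − 0.95^(k+1):
- k = 3: 1 − 0.95^4 = 18.5%
- k = 6: 1 − 0.95^7 = 30.2%

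This is too high, because the total is built from the subscales.

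**Step 2, simulation with dependence.** In each of 40,000 trials per cell, draw k normal change scores with correlation ρ for 60 women, add their sum as the total, compute t = mean change ÷ (SD of change ÷ √60) for each, and count trials in which any |t| exceeds the two-sided 5% point on 59 degrees of freedom.

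| ρ | 0 | 0.3 | 0.5 | 0.7 | 0.9 |
|---|---|---|---|---|---|
| k = 3 | 16.1% | 14.4% | 12.7% | 11.0% | 8.4% |
| k = 6 | 28.3% | 24.7% | 20.8% | 16.9% | 10.9% |

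Sample size hardly matters: with n = 30 the two extremes are 8.8% and 28.6%. At ρ = 0.95 with k = 3 the rate is 7.2%, still above 5%.

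**Step 3, the hardest case to interpret.** A false significant subscale beside a non-significant total occurs in 3.5–11.1% of trials with 3 subscales and 5.9–23.1% with 6 (low ends at ρ = 0.9, high ends at ρ = 0). False changes in the direction of improvement are about half of the rates in Step 2: 4–8% and 5–15%.

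**Step 4, what the remedies do (pooled, n = 60).**
- One primary test on the total: 5% by construction.
- Holm on the subscales, only if the total is significant: any false FSFI claim needs a false total, so 5%; simulated 4.8–5.0%.
- Holm across the total and all subscales: at most 5%.
- Total at 0.05 plus a separate Holm family for the subscales: 5–9%, so this does not hold the level.

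**Step 5, what the remedies cost.** The change detectable with 80% power, in SDs of the change score (paired t, n = 60), is 0.37 at 0.05 and 0.46 at 0.05/6 = 0.0083. The same calculation at 0.05/7 = 0.0071, the first Holm step for the total and 6 subscales together, gives 0.47. If exactly one of 6 subscales truly changes by 0.46 SD, the chance of claiming it is about 78% with Holm across all seven scores and 9–28% with the gated rule.

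**Step 6, by contraceptive group.** If a 5% rule is run once in each group, the chance of a false claim in at least one is 1 − 0.95² = 9.75%, about 10%. With alpha split to 0.025 per group it is 1 − 0.975² = 4.9%. Unadjusted testing of every FSFI score in both groups of 30 gives about 20–30% (k = 3) or 27–49% (k = 6) for ρ from 0.8 down to 0.

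**The case against.** **The high end is extreme.** This stands. The 28% needs six uncorrelated subscales of one questionnaire. Correlation drives the figure and the documents do not give it, so the range must be quoted with it. A reader might take 28% as the expected rate; nothing in the documents supports that.

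**The tests are disclosed.** This also stands in part. The SAP lists the total, the subscales and vitamin D openly, so the defect is a missing ranking and a missing rule, not concealment. Nor does the SAP label any test exploratory; it plans to judge "statistical significance of change scores".

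**The protocol's background might seem to invite picking a subscale.** One sentence says "the domains of desire and arousal are most commonly affected" and the next reports that women with PCOS "differed significantly with lower orgasm/completion scores than control women". A reader might infer that a subscale chosen afterwards could be passed off as planned. The documents do not support this. The orgasm/completion result comes from a different questionnaire, the CSFQ; the desire and arousal sentence names no instrument; and neither document lists the FSFI subscales. The point does not rely on it.

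**The 5% depends on pooling.** Correct. Objective 2 speaks of treatment with and without hormonal contraceptives, and the SAP does not say whether tests are pooled or by group. The remedy has to say which.

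**A strict gate is a choice, not a necessity.** Correct. It protects the total at a heavy price for a change confined to one domain, and Holm across all scores is a sound alternative.

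**Regression to the mean may matter more.** It may. Suppose entry takes the lowest 60% of FSFI totals (borrowing the background's figure for sexual dysfunction) and the retest correlation is 0.7 to 0.9, both assumptions. With no effect, the total alone then shows a false improvement in 51% down to 20% of trials. That is a separate problem and does not remove this one.

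**Conclusion.** The concern holds in this form: the SAP plans significance tests on the FSFI total and subscales with no primary FSFI outcome, alpha or multiplicity rule, and the risk of at least one false significant FSFI change is therefore above the per-test level. The estimate is about 8–28%, and 17–21% with 6 subscales at correlation 0.5–0.7, against 5% for a single primary test. It rests on the assumptions listed in the working. The direction holds across all of them; the exact size does not come from the documents. Adding the vitamin D test or testing by group would raise it.

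A reader might go further and infer that the remedy caps false claims of improvement at 5%. It does not. It controls multiplicity only; because women enter on poor scores from the same instrument and there is no untreated control, the single primary test can itself show improvement without any treatment effect.

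**What to change.** Add to the SAP, before results are seen, wording to this effect:

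- The change in FSFI total from baseline to 6 months, in all participants pooled, is the single primary outcome, tested at two-sided 0.05.
- Subscale changes and any results by contraceptive group are secondary. They are reported as mean change with 95% CI and cannot by themselves support a claim on objective 2.
- Vitamin D level is a separate secondary outcome.

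The total is the natural choice because objective 2 and the inclusion criterion both refer to sexual dysfunction without singling out a domain. This is a reading of those passages; a sponsor with a specific domain hypothesis could name that domain instead, provided that it does so in advance.

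If confirmatory subscale claims are wanted, pre-specify one of two rules:

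1. Holm across the total and all subscales. A change in a single domain keeps good power, but the total faces a stricter threshold (with 6 subscales, 0.0071 at the first step, which raises its detectable change from 0.37 to 0.47 SD).
2. Holm on the subscales only if the total is significant. The total loses nothing, but a change in a single domain will usually go unclaimed.

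If the primary test is instead run within each contraceptive group, split alpha across the two groups. At n = 30 the detectable change is 0.53 SD at 0.05, and larger once alpha is split.

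The cost is a few sentences and no new data. The downside is that subscale results lose stand-alone significance claims or need smaller p-values; their estimates and intervals are still reported. Regression to the mean and the missing untreated control need their own remedy.

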STUDY OUTLINE

TITLE: Evaluation of Vitamin D With And Without Hormonal Contraception on Sexual Function in Women With Polycystic Ovary Syndrome

INVESTIGATORS: [name], MMM; [name]; [name], [name]; [name]

NCT02865187

SUMMARY:

Polycystic ovary syndrome (PCOS) is the most common endocrine disorder among reproductive age women with a prevalence as high as 15%. The clinical symptoms of PCOS including menstrual dysfunction, infertility, hirsutism, alopecia, acne, and the possible increased risk of diabetes and cardiovascular disease have been reported to be significant contributors to psychological morbidity and impact health-related quality of life. For women with PCOS, the changes in physical appearance and the associated mood disorders appear to be deleterious for sexual function.

Vitamin D deficiency (<20 ng/ml serum concentration of 25[OH]D), which affects from 67% to 85% of women,⁴ is closely linked to symptoms of PCOS. The main physiologic role of vitamin D is to regulate calcium and phosphorus homeostasis and to promote bone health. Although there has been an increase in awareness of the importance of sexual dysfunction and QoL in women with PCOS, few studies have evaluated the outcomes of treatment for PCOS upon sexual and subjective health status of women.

The goals of this study are:

1. To evaluate the prevalence of sexual dysfunction (SDy) in women with Polycystic Ovarian Syndrome (PCOS)

2. To determine the effects of Vitamin D therapy, with and without hormonal contraceptives, on SDy in women with PCOS in the absence of depression.

METHODS:

The study will enroll 60 women diagnosed with PCOS and reporting SDy at the Wright State Physicians (WSP) OB-GYN Practice and the WSP Family Medicine Practice.

All participants will take vitamin D 600IU/day and will choose between hormonal and non-hormonal contraceptive methods (target of 30 participants in each group). Participants will complete three study visits (Initial, Month 3, and Month 6). Vitamin D levels will be drawn at the beginning of the study and again at 3 and 6 months after initiation of vitamin D therapy. Each participant will be asked to complete the Female Sexual Function Index (FSFI) and the Beck Depression Inventory (BDI) prior to initiation of treatment and again at 6 months.

TITLE: Evaluation of Vitamin D With And Without Hormonal Contraception on Sexual Function in Women With Polycystic Ovary Syndrome

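### The SAP's paired t-tests make no use of contraceptive group, so the part of Objective 2 about hormonal contraceptives need not be answered

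*SAP*

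**What the plan says.** Protocol Objective 2, given in the Summary and again under Objectives, is "To determine the effects of Vitamin D therapy, with and without hormonal contraceptives, on SDy in women with PCOS in the absence of depression". The Background closes with a related aim, to "assess the impact of treatment using oral contraceptives with Vitamin D on SDy in absence of depression".

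Under Methods, "All participants will take vitamin D 600IU/day", and participants "will choose between hormonal and non-hormonal contraceptive methods (target of 30 participants in each group"). The enrolment target is 60. Group is therefore chosen by the woman, and vitamin D is common to both groups. The inclusion criteria require that women "Report SDy according to the FSFI".

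The SAP's analysis text is two sentences long. It plans "comparison of baseline with 6 month scores on FSFI total and subscale scores" and the same comparison for vitamin D levels. The method is one line: "Paired t-test will be used to determine degree of change and statistical significance of change scores". Apart from the study title, the SAP does not mention contraception. The protocol has no statistical section that adds a group analysis.

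**The concern.** Contraceptive method is the only grouping factor in the design, and it appears in the title and in the study's only treatment objective. The analysis does not use it. Objective 2 can be read in two ways:

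- **Change on vitamin D within each contraceptive group.** This needs the paired tests to be run by group, and the SAP does not say that they are.
- **A contrast between the groups.** This needs an estimate of the difference in change. A paired test compares each woman with herself and cannot supply one.

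A pooled analysis satisfies the SAP under both readings and answers neither. A pooled improvement could come from one group alone, and opposite changes could cancel. If a group analysis is added once the data have been seen, it is not prespecified.

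**Working it through.** The documents give no alpha, power, SD, correlation, target effect or dropout rate, so the plan has no figure to reproduce. The finding rests on the text. The numbers below show its size under these assumptions: two-sided alpha 0.05, normal changes, equal SD of change in both groups, and no dropout unless stated. Effects are in SDs of within-group 6-month FSFI change.

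**1. What a pooled test can show.** Expected pooled change = (n_H·δ_H + n_N·δ_N)/(n_H + n_N), where H is hormonal and N is non-hormonal.

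- 0.5 SD in hormonal users only: (30×0.5 + 30×0)/60 = 0.25.
- 0.25 SD in both groups: (30×0.25 + 30×0.25)/60 = 0.25.
- 0.5 SD in hormonal users only, 40 v 20: (40×0.5 + 20×0)/60 = 0.33.
- Opposite changes of 0.5 SD: (30×0.5 − 30×0.5)/60 = 0.

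Simulated rejection rates, 30 + 30 women:

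| True change, H / N | Pooled paired test | Between-group test |
|---|---|---|
| 0.4 / 0.4 | 86% | 5% |
| 0.8 / 0 | 83% | 86% |
| 0 / 0.8 | 83% | 86% |
| 0.5 / −0.5 | 3% | 97% |

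The pooled test behaves almost alike in the first three rows, although the group results are very different.

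**2. Separate tests do not give the contrast.** With equal true changes of 0.4 SD, one group is significant and the other is not in 49% of simulated trials. Comparing two p-values would often suggest a group difference that does not exist.

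**3. Precision of the added estimates.**

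- Within one group of 30: t(29)/√30 = 2.045/5.477 = ±0.37 SD.
- Difference, 30 v 30: t(58)×√(2/30) = 2.002×0.258 = ±0.52 SD. Power of 80% needs 0.74 SD, and power at 0.5 SD is 48%.
- Difference, 24 v 24 (an assumed 20% dropout): ±0.58 SD. Power of 80% needs 0.83 SD, and power at 0.5 SD is 40%.
- Difference, 40 v 20: t(58)×√(1/40 + 1/20) = ±0.55 SD. Power of 80% needs 0.78 SD.
- Baseline-adjusted difference, 30 v 30, in women selected from the lowest 60% of scores (simulated): ±0.48, ±0.49 and ±0.51 SD at baseline-to-6-month correlations of 0.4, 0.6 and 0.8.

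**4. Why by-group changes need an uncontrolled label.** Assume the entry FSFI is also the baseline, scores are normal, the lowest 60% qualify and nothing truly changes. The 60% borrows the Background's figure of "a large number of women with PCOS (60%) reporting sexual dysfunction" as an illustration. A standard normal below its 60th percentile has mean −0.644 and variance 0.422. Expected change is (1−r)×0.644, and the SD of change is √((1−r)²×0.422 + 1 − r²).

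- r = 0.6: 0.258/0.841 = 0.31 SD of apparent improvement, significant in 37% of groups of 30 and 65% of pooled samples of 60.
- r = 0.8: 0.129/0.614 = 0.21 SD, significant in 20% and 36%.

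These rates depend heavily on the share who qualify. At r = 0.6 and n = 30, the rate is about 85% if 30% qualify and about 7% if 90% qualify.

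**The case against.** The strongest reply is that the SAP is silent rather than wrong. It does not say the tests are pooled, and running them in each group of 30 would contradict nothing. This is why the finding says that the question need not be answered, not that it cannot be. It does not remove the gap: a pooled test complies equally well, and by-group tests still give no contrast.

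The SAP's list has an item numbered 1 and no item 2, so something may have been lost. That is a fair caution. No text in either document supplies a group analysis, and if an item was dropped it has to be restored.

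Objective 2 is also about vitamin D, which every woman takes, so a difference between self-chosen groups is not a vitamin D effect. That is correct, and it fixes how the difference must be labelled. The Background's aim, however, makes contraceptives with vitamin D the treatment under study, so the contrast is within scope.

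Low power is real and favours intervals over significance tests. Regression to the mean affects pooled and by-group tests alike, so it is no evidence that group was omitted. Here it supports only the uncontrolled label.

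**Conclusion.** The concern holds, and the SAP must be changed. Objective 2 and the two-group design turn on contraceptive method, the SAP's analysis never uses it, and neither document fills the gap. Followed as written, the plan can end with no result for that part of its treatment objective. This conclusion comes from the text and depends on none of the assumed inputs. Under those inputs, pooling hides a change confined to one group and misses opposite changes of 0.5 SD about 97% of the time. Confidence is high.

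**What to change.** Add to the SAP:

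1. Six-month change in FSFI total and subscales, reported separately for each contraceptive group with 95% CIs. Label these changes uncontrolled: all women take vitamin D and entry requires sexual dysfunction on the FSFI, so regression to the mean or time could explain improvement.
2. The between-group difference in 6-month FSFI total change with its 95% CI, from one prespecified model adjusted for baseline FSFI. Adjustment for baseline Beck Depression Inventory score is optional, but the SAP should say now whether it is included.
3. The unadjusted difference in change scores as a sensitivity analysis, since the two can differ if the self-chosen groups differ at baseline.
4. A statement that this difference is an observational association with contraceptive method, because women choose their group, and that interpretation rests on estimates and intervals.

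The cost is a few sentences, one model and one sensitivity analysis on data already planned. No visit, measurement or participant is added. The price in precision is the roughly ±0.5 SD interval shown in the working, which the SAP should acknowledge.

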The PI is responsible for protection of human subjects. This protocol will be reviewed by the WSU Institutional Review Board. Only subjects who meet study eligibility criteria will be enrolled. All eligible participants will have the study explained to them. The informed consent process will be conducted appropriately and the informed consent will be obtained prior to proceeding with any study procedures.

The primary physician or the Principal Investigator and research associates will be the individuals obtaining informed consent from patients. They will be uniform in their explanations of the nature of the study to all patients who fit the selection criteria. Those patients interested in

participating will be given time to read over the informed consent. The patients will be asked either in the clinic to be involved in the study. After the informed consent is reviewed by the patient any remaining questions will be answered.

Adverse events will be reviewed and evaluated by the PI throughout the study. In the event that any additional diagnoses are obtained during this study, the primary physician for the patient will be notified. It will be their responsibility to notify the patient of these diagnoses and any changes to management that may result.

Subjects' confidentiality will be protected. Participants will be assigned a unique identification (ID) number for the study that will be used on data collection forms rather than subjects' names. Only the minimum data necessary to conduct the study and meet the objectives will be collected. Data will be stored in a secure database (REDCap¹⁹) that uses a unique username and password for each team member. Data will be de-identified prior to analysis.

SIGNIFICANCE OF THE STUDY IN RELATION TO HUMAN HEALTH (BENEFITS):

PCOS is the most common reproductive endocrine disorder that has a number of health quality of life issues. The benefit of this study will be to identify SDy which is often overlooked and may potentially be helped with Vit D and/or birth control.

POTENTIAL HAZARDS (RISKS):

The study questionnaires may evoke stressful feelings taking a psychosocial questionnaire. In addition, there are rare potential risks related to OCPs including deep venous thrombosis, and stroke.

Serious side effects of vitamin D include allergic reactions, swelling of the face, throat, and tongue, dizziness, irregular or racing heart beat, dry mouth, headache, vomiting, weakness and lack of energy, and fatigue

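### The SAP does not define the baseline FSFI; if it is the qualifying score, as seems most natural, regression to the mean biases the 6-month change upward and the paired tests cannot detect it

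*SAP*

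**What the plan says.** - **Entry.** Inclusion criterion 3 in the protocol is "Report SDy according to the FSFI". It gives no cut-off and does not say whether the total or a subscale decides. Methods plans to "enroll 60 women diagnosed with PCOS and reporting SDy".
- **Measurement times.** Methods has each participant "complete the Female Sexual Function Index (FSFI) and the Beck Depression Inventory (BDI) prior to initiation of treatment and again at 6 months". The visits are Initial, Month 3 and Month 6. No screening visit and no second pre-treatment FSFI are described.
- **Analysis.** The SAP compares baseline with 6 months on the FSFI total and subscales, and on vitamin D levels: "Paired t-test will be used to determine degree of change and statistical significance of change scores". It does not define baseline, and it plans no comparison between the contraceptive groups. It does not say whether the tests pool all women or are run within each group.
- **Control.** Methods gives vitamin D to every participant and lets her choose her contraceptive method, with a target of 30 per group. Objective 2 asks for the effects of vitamin D, with and without hormonal contraception.

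**The concern.** An FSFI score contains within-woman variation. Women selected because one score was low include some who were low by chance on that day, and on average they score higher when measured again. If the selecting score is also the baseline, that rise is counted as change on treatment.

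A paired t-test has zero change as its null. It would show the rise as improvement, and nothing else in the plan would separate the two, since no group goes without vitamin D. The SAP sentence itself claims only change. The risk arises when a significant FSFI change is used to answer objective 2, which is about effects.

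**Working it through.** The documents give no FSFI cut-off, SD, correlation, significance level or power calculation, so there is no planned figure to reproduce. What follows is a range under stated assumptions.

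**Inputs**
- n = 60 pooled, or 30 per group (protocol, Methods).
- Share of FSFI-tested women below the cut-off, p: not given. The protocol's Background cites 60% of women with PCOS reporting sexual dysfunction, but does not tie this to the FSFI. Because the study seeks women reporting SDy, p could be well above 60%. Values of 60%, 80%, 90% and 95% are used.
- Assumed: entry is decided by the score being tested; scores are normal; test-retest correlation r = 0.6, 0.7, 0.8, 0.9 among all tested women; two-sided 0.05 (so 2.5% nominal in the improvement direction); everyone completes; no treatment effect.

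**Expected rise with no effect**, in SDs of all tested women:

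shift = (1 − r) × φ(z)/Φ(z), where Φ(z) = p.

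- p = 60%: φ/Φ = 0.644. Shift = 0.4 × 0.644 = 0.26 at r = 0.6; then 0.19, 0.13 and 0.06 at r = 0.7, 0.8 and 0.9.
- p = 95%: φ/Φ = 0.109. Shift = 0.4 × 0.109 = 0.04 at r = 0.6, falling to 0.1 × 0.109 = 0.01 at r = 0.9.

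**Hand check of one cell** (p = 60%, r = 0.6, n = 60). Here z = 0.253. The variance of the selected scores is 1 − 0.253 × 0.644 − 0.644² = 0.422. The variance of the change is 0.4² × 0.422 + (1 − 0.6²) = 0.708, so its SD is 0.841 and its standard error is 0.841/√60 = 0.109. The shift is 0.258/0.109 = 2.37 standard errors against a critical value of 2.00. Φ(2.37 − 2.00) = Φ(0.37), about 0.64.

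**Simulated rate of significant improvement with no effect** (r = 0.6/0.7/0.8/0.9; nominal 2.5%):

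| Share below cut-off | All 60 pooled | Group of 30 |
|---|---|---|
| 60% | 65/51/36/20% | 37/28/20/12% |
| 90% | 10/8/7/5% | 7/6/5/4% |
| 95% | 6/5/4/4% | 4/4/4/3% |

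At 80% the rates run from about 24% to 9% pooled and from 14% to 6% in a group of 30. With no selection the simulation returns about 2.5%. Smaller groups lower the error rate but not the bias in SD units.

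**If a separate pre-treatment FSFI is the baseline.** The residual rise is (r between screening and repeat − r between screening and 6 months) × φ/Φ. The simulation sets the repeat-to-6-month correlation equal to the screening-to-6-month one.
- Equal correlations: zero rise, and about 2.5% false improvement.
- 0.8 then 0.7, n = 60: 0.1 × 0.644 = 0.06 SD and about 9% at p = 60%; about 3% at p = 95%.
- 0.9 then 0.6, n = 60: 0.3 × 0.644 = 0.19 SD and about 40% at p = 60%; about 5% at p = 95%. A single FSFI with the same 6-month r of 0.6 gives 65% at p = 60%.

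So a repeat lowers the bias in these cases but does not always remove it.

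**The case against.** **The double use of one score is inferred.** Recruitment has women "approached at their clinic visit with the physician if the patient meets selection criteria", and Human Subjects Protection says "the informed consent will be obtained prior to proceeding with any study procedures". Together these allow an FSFI known before consent followed by a separate study FSFI. With equal correlations that design has the nominal error rate. This stands. A reader might infer that the baseline is shown to be biased; the documents show only that it is undefined. One pre-treatment FSFI and no screening visit still make the double use the more natural reading.

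**The size is undetermined.** This also stands. A reader might take 65% as this trial's false-positive rate. It needs all women pooled, the lowest r in the range and a 60% share taken from a background figure. If nearly every tested woman qualifies, the inflation is a few percentage points at most.

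**Entry may not rest on the total.** Correct. The bias falls directly on whichever score decides entry, and on other FSFI scores through their correlation with it. The table does not apply directly to the latter.

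**The uncontrolled design is the larger limit.** Placebo, seasonal and time effects would remain even with a sound baseline. Comparing the contraceptive groups would partly cancel regression to the mean, but the groups are self-chosen and both take vitamin D. This does not answer the point; it is why the wording of the conclusion needs limiting as well as the baseline.

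**Conclusion.** The point holds conditionally. The SAP leaves baseline undefined. On the most natural reading the qualifying FSFI fills that role, and the expected change is then above zero for any r below 1 with no treatment effect. The planned paired tests of the FSFI total and subscales cannot separate that rise from an effect.

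The direction follows from selection on a low, imperfectly repeatable score. The size does not follow from the documents: under the assumptions above, the spurious rise runs from 0.26 SD to 0.01 SD, and false improvement from 65% to about 3%, against 2.5%. The point should not be extended to vitamin D levels, because no entry criterion uses them. It is a cheap improvement worth making; it does not show that a result from this trial would be wrong.

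**What to change.** 1. **Define the baseline FSFI in the protocol and SAP.** Use the qualifying FSFI for eligibility only. Take a second self-completed FSFI after consent and before vitamin D starts, do not re-apply the cut-off, and use that score as the analysis baseline. State that this reduces the bias, and removes it only if the screening score correlates equally with the repeat and with the 6-month score; a repeat taken very close to the first may remove less.
2. **Limit the conclusion in the SAP**, for example: *Paired FSFI results are reported as uncontrolled change during treatment. A test against zero change will not be taken as evidence of a vitamin D effect. Regression to the mean, placebo, seasonal and time effects are not removed by this design.*

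Estimating the shift from screened women who do not qualify is not proposed. It sits badly with the protocol's statements "Only subjects who meet study eligibility criteria will be enrolled" and "Only the minimum data necessary to conduct the study and meet the objectives will be collected".

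**Cost.** Step 2 is wording only, and so is step 1 if a separate study FSFI is already intended. Otherwise step 1 needs one extra form, a slightly later start and a protocol amendment. The downside is a less favourable-looking conclusion.
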